Primary Objective: The primary objective of this study is to determine whether anodal (A-tDCS) applied to L IFG along with verb therapy can improve naming outcome in individuals with PPA. A randomized, double-blind, sham controlled, within-subject crossover design will be used because this allows each participant to serve as their own control. Participants will be randomly assigned to receive either a tDCS intervention period followed by a sham intervention period, or sham followed by tDCS. Participants will receive 15 training sessions within the tDCS intervention period and 15 sessions within the sham intervention period. Each participant will receive 3-5 sessions per week depending on their preference and availability. The tDCS and sham intervention periods will be separated by an 8 week "wash out period". Language will be evaluated before therapy, one week after therapy, and 8 weeks after therapy for each intervention period.

Aim 1: To evaluate the effects of A-tDCS applied to left IFG during VNeST therapy on word retrieval of trained verbs, and generalization to untrained verbs and nouns in a randomized double-blind, sham controlled, within-subject crossover trial design. The Object Action Naming Battery (OANB) (Druks, 2000) will be used to evaluate verb and noun retrieval by testing participants at baseline and at 1 and 8 weeks post-treatment. The OANB tests confrontational naming of 162 objects and 100 actions. The verbs on the OANB will be separated into trained (OANBtrained) and untrained (OANBuntrained) verbs, which will be personalized for each participant, in order to evaluate generalization. The primary outcome variable will be change in naming accuracy of OANBtrained verbs. Secondary outcome variables will be change in naming accuracy of OANBuntrained verbs and untrained nouns (OANBnouns), as well as

Hypothesis 1A. Anodal tDCS (A-tDCS) plus VNeST therapy (A-tDCS+therapy) will significantly improve word retrieval of trained transitive verbs (from baseline to 1 week and 8 weeks post treatment).

Hypothesis 1B. A-tDCS+therapy will generalize to other untreated verbs and nouns from baseline to 1 week and 8 weeks post treatment.

Hypothesis 1C. Combined A-tDCS+therapy will result in greater improvement in functional communication skills compared to sham+therapy.

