PPA is a neurological syndrome characterized by the progressive impairment of language functioning caused by neurodegenerative diseases including frontotemporal lobar degeneration and Alzheimer's disease (Gorno-Tempini et al., 2011). In the early stages of PPA cognitive skills, like episodic memory, are typically preserved. There are three subtypes of PPA, which each have a different pattern of atrophy and distinct profile of language deficits. The semantic variant (svPPA) is defined by impaired naming and difficulty understanding single words, with preserved speech articulation, and is associated with bilateral atrophy in ventrolateral anterior temporal lobes that is typically greater in the left hemisphere. The non-fluent/agrammatic variant (nfvPPA) is characterized by agrammatic language production or apraxia of speech with atrophy in left posterior frontal and insular regions. Word comprehension is generally spared in the early stages of nfvPPA and lvPPA. Individuals with the logopenic variant (lvPPA) experience both word retrieval and sentence repetition deficits along with atrophy in left temporoparietal areas. Word retrieval deficits are present in the early stages of all PPA subtypes, although verbs tend to be more impacted in nfvPPA, and nouns in svPPA, with no distinction between nouns and verbs in lvPPA (Hillis et al., 2006, 2004; Thompson et al., 2012). This pattern is likely because verb retrieval is reliant on left frontal regions (den Ouden, Fix, Parrish, & Thompson, 2009). These debilitating language deficits interfere with daily life and therefore have many negative consequences for quality of life in PPA patients (Kortte & Rogalski, 2013). Yet, there are very few studies that have investigated language therapy to improve, or at the very least maintain word retrieval abilities, and ideally slow the progression of language loss. Although most of these studies have been single and dual case studies they do show that naming therapy can be used successfully in PPA and therefore more research is needed to determine which specific types of treatment will be most beneficial for individuals with different types of PPA. Thus far, approaches such as the picture naming repetition (Graham, Patterson, Pratt, & Hodges, 1999), reading and writing labels associated with pictures (Meyer et al., 2016), and generative naming where participants name members of a category (Beeson et al., 2011), have been found to be effective at maintaining language functions for a few months. Because PPA is a neurodegenerative disorder, and thus their language skills are expected to decline, reducing the rate of decline is an important goal.

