
The ultimate goal of most language interventions is for treatment effects to generalize to untrained items. Studies investigating complexity theory in post-stroke aphasia demonstrate that training more complex items in language therapy can generalize to simpler items. For example, several studies have found that training non-canonical sentences with complex syntax will generalize to untreated simpler syntactic structures (Mack & Thompson, 2017; Thompson et al., 2003) and training atypical exemplars during naming therapy will generalize to typical items but not vice versa (Kiran & Thompson, 2003). Evidence shows that VNeST therapy for word retrieval generalizes to untrained verbs and nouns, and improves sentence production as well (Edmonds, 2016). Participants are given transitive verbs, which require two arguments, that are used to build sentences by adding appropriate noun arguments that fulfill the thematic roles of the agent (the doer of the action) and the theme (the receiver of the action) (Edmonds et al., 2014). This type of therapy, which uses the building of sentences to treat word-level deficits, has not been investigated in PPA. Given the treatment success seen in individuals with post-stroke aphasia in terms of

generalization (Edmonds, 2016), it is important to investigate whether individuals with PPA could also benefit from this complexity strategy.

A growing number of studies investigating neurostimulation via tDCS have shown very promising results in post-stroke aphasia (Baker et al., 2010; Fridriksson et al., 2011). Similarly, the few studies investigating tDCS in PPA have also suggested it can augment the benefits of language therapy alone. For example, Tsapkini and colleagues (Tsapkini et al., 2015, 2014) have found that A-tDCS applied to left IFG paired with word-level spelling therapy improved written word production, and critically these effects generalized to untrained items and were sustained over the course of two months post-treatment conclusion.

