Visit 3-4: These sessions involve detailed language testing (see below) including computerized naming assessments. This battery will be the baseline language testing. A screening task will be administered prior to the baseline language testing. Participants must achieve at least 65% accuracy on screening task (comparable to treatment task) on 1 of 3 attempts. The screening test is administered to ensure that the participant understands the treatment task requirement. The probability that a patient will achieve $>65\%$ accuracy by chance on each of the three tries is low: $p<0.05$. If a participant is unable to reach this level of accuracy, study enrollment will be discontinued. A naming test will also be administered as part of baseline testing examining the ability to name nouns and verbs from pictures. Participants who's correct naming score exceeds an average of 80% accuracy will be excluded to leave at least a 20% improvement margin. That is, participants who already score close to ceiling may have limited room for naming improvement.

Visit 5-19: These sessions will involve the treatment sessions for the first intervention period. Prior to the start of treatment, participants will be randomly assigned to receive either "tDCS then sham" or "sham then tDCS". For example, if a participant is randomly assigned to received "tDCS then sham", the first intervention period of 15 sessions will be tDCS+ language treatment and the second intervention period will be 15 sessions of sham + language treatment.

Date: 01/11/2019
Principal Investigator: [name]
Application Number: IRB00174879

Visit 20: This visit will involve 1 week post treatment language testing. This visit will be similar to Visits 3-4.

Visit 21: 8-week follow up visit. Testing during this session will be considered as baseline testing for phase 2 intervention.

Visit 22-36: These sessions will involve the treatment sessions for the second intervention period. The opposite tDCS condition will be implemented here. For example, if a participant is randomly assigned to received “tDCS then sham”, the second intervention period will be 15 sessions of sham + language treatment.

Visit 37: 1-week follow up language testing after second intervention period.

Visit 38: 8-week follow up language testing after second intervention period.

Procedures for Screening (Visit 1)

The following procedures will be performed:

1. Administer the tDCS safety screening and MRI safety screening

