Procedures for the Naming Assessments (Visits 1, 2 & all follow up evaluations)

The following procedures will be performed during Visits 1, 2, and each follow-up evaluation:

1. Turn on the laptop computer and position in front of the participant.
2. Set up and start internal web-camera for audio-visual recording, to allow inter-rater reliability assessment. Administer the OANB. Instruct the participant to overtly name each picture as soon as it is displayed. Trials will end following a response or after 10-seconds have elapsed, in which the administrator will say the correct picture name in order to discourage perseveration on subsequent trials.
3. Stop web-camera and save video file for later scoring of naming.

Procedures for the “Cookie Theft” Picture Discourse Analysis and Depression Scale (Visit 3, 20, 21, 37 and 38). The following procedures will be performed during Visits 3 (baseline), 20 (1-week after intervention period 1), 20 (8-week follow up/baseline testing for intervention period 2), 37 (1-week after intervention period 2), and 38 (8-weeks after intervention period 2).

1. The “Cookie Theft” is to be completed following the administration of the naming assessments, so the laptop computer and web-camera set-up will need to remain for this portion of the assessment.
2. Place the Cookie Theft picture in front of the participant.
3. Tell the participant, “Tell me everything you see going on in this picture. Whenever possible try to use full sentences.
4. Stop web-camera and save video file for later transcription.

Procedures for Treatment (Visit 5-19) for intervention period 1 and Visits 22-36 for intervention period 2

The following procedures will be performed:

1. Place a scalp cap, which contains scalp sites labeled according to the 10-20 system, on participant’s head. Locate the “F5” label, which is the label corresponding to the left IFG.
2. Soak the 2 sponge electrodes in saline solution and place inside rubber electrode holders.
3. Place the anode electrode under the designated area (“F5”) against the scalp, and reference electrode on the right deltoid muscle.
4. Connect the electrode cables to the Soterix tDCS device.

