For Aim 1, Hypothesis 1a This hypothesis states that Anodal tDCS (A-tDCS) plus VNeST therapy (A-tDCS+therapy) will significantly improve word retrieval of trained transitive verbs (from baseline to 1 week and 8 weeks post treatment). In the proposed study each participant will either receive tDCS (T) in the first intervention period followed by sham (S) in the second period (order = TS), or they will receive sham in the first period followed by tDCS (order = ST). For each participant, i , we will measure the change in word retrieval on the OANBtrained due to real tDCS stimulation by subtracting word retrieval performance accuracy on the OANBtrained before tDCS stimulation from the testing period 1 week following tDCS stimulation ($\delta Y_{i,tDCS}$). The identical measure will be computed for sham stimulation ($\delta Y_{i,sham}$). The data will be analyzed ($order_i, \delta Y_{i,tDCS}, \delta Y_{i,sham}$) for participants $i = 1, \dots, n$. Three models will be evaluated: the model of tDCS vs. sham, the model that adds the period effect, and the model that adds the interaction (a carryover effect). The predictive accuracy of these 3 models will be compared using the leave-one-out cross-validation R^2 . The model that best fits the data (the model with the highest R^2) will then be used to estimate the effect of tDCS relative to sham. This procedure will be repeated to determine changes from baseline to a period 8 weeks after treatment conclusion.

Sample Size Determination

We expect to enroll at least 50 participants with PPA over five years, and expect 45-50 will complete the study. This sample size is based on data collected from a separate study, IRB protocol number NA_00078932, PI [name]. *The effect size for anodal tDCS stimulation was 0.6 for trained items and 1.5 for untrained items.* We determined the number of participants to study, in order for the analysis to have 80% power to detect an effect size as low as 0.6. Allowing for 10% attrition, a sample size of 50 was chosen.

Missing Data

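### Visit 21 is both the period-1 8-week outcome and the period-2 baseline, so the planned 8-week contrast overstates the tDCS effect if that effect fades between Visits 21 and 38

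*Combined protocol and SAP*

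**What the plan says.** - **Design (section 2, Primary Objective).** Participants are randomised to tDCS then sham, or sham then tDCS. "The tDCS and sham intervention periods will be separated by an 8 week" interval, which the plan labels a washout.
- **Visit 21 (section 4a).** It is listed as the 8-week follow-up of the first period, and "Testing during this session will be considered as baseline testing for phase 2 intervention".
- **Hypothesis 1A (section 2).** Active stimulation plus therapy "will significantly improve word retrieval of trained transitive verbs (from baseline to 1 week and 8 weeks post treatment". The gain is thus expected to be present at the visit that serves as the next baseline.
- **Background (section 3).** Of earlier tDCS work in PPA the plan says "critically these effects generalized to untrained items and were sustained over the course of two months post-treatment conclusion". Naming therapies without stimulation are described as "effective at maintaining language functions for a few months".
- **Analysis (section 7c, Hypothesis 1a).** For each participant, post-minus-pre change is computed separately for the tDCS and sham periods. Three models are compared: treatment; treatment plus period; and a third that adds an interaction, described as carryover. The one with the highest leave-one-out R-squared gives the estimate. Then: "This procedure will be repeated to determine changes from baseline to a period 8 weeks after treatment conclusion".
- **Items (section 2, Aim 1).** "The verbs on the OANB will be separated into trained (OANBtrained) and untrained (OANBuntrained) verbs", with the split personalised. The plan does not say whether one trained list serves both periods.
- **Testing (section 4a, Naming Assessments).** "The following procedures will be performed during Visits 1, 2, and each follow-up evaluation", so naming scores exist at the first baseline and at Visits 20, 21, 37 and 38.

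**The concern.** Visit 21 enters the analysis twice with opposite signs: it is the outcome in the period-1 change and the value subtracted in the period-2 change. In the tDCS-first order, a gain still present at Visit 21 raises the period-2 baseline. Whatever part of that gain is lost by Visit 38 then counts as deterioration under sham, and the tDCS-minus-sham difference grows.

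The 8-week result is what would support a claim of sustained benefit, and section 7c (Missing Data) justifies the two-month interval as long enough to judge sustainability. The possible error runs against that purpose, because faster fading after Visit 21 makes the 8-week effect look relatively larger. The same analysis is applied to untrained verbs and nouns, so the generalisation results are exposed as well.

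**Working it through.** The plan gives no figure for this contrast, so there is none to reproduce. Its sample size does not enter the algebra.

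**Inputs from the documents.** Visit roles are from section 4a. Treatment lasts 3–5 weeks per period (section 4b). Visit 37 is therefore 8 + (3 to 5) + 1 = 12–14 weeks after period 1 ends, and Visit 38 is 8 + (3 to 5) + 8 = 19–21 weeks after.

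**Assumed.** 1:1 allocation (the ratio is not stated) and the same items scored at every visit.

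**Step 1: what the contrast measures.** Write V for the score at a visit, V3 for the first baseline, and D for the tDCS-first minus sham-first difference.
- tDCS first: (V21 − V3) − (V38 − V21) = 2·V21 − V3 − V38
- Sham first: (V38 − V21) − (V21 − V3) = V38 − 2·V21 + V3
- Mean of the two orders: D21 − D38/2 − D3/2, and D3 is zero in expectation under randomisation. The contrast is **D21 − D38/2**. Decline common to both orders cancels.

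**Step 2: in terms of the effect.** Let E and S be the gains t weeks after tDCS and sham treatment, and N = E − S. N20 and N13 stand for what is left at Visits 38 and 37. Suppose gains add and second-period training does not alter the fading of the first gain.
- D21 = N8, and D38 = (E20 + S8) − (S20 + E8) = N20 − N8
- 8-week contrast = N8 − (N20 − N8)/2 = **1.5·N8 − 0.5·N20**
- 1-week contrast, by the same route = **N1 + 0.5·(N8 − N13)**

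The ratio of the 8-week contrast to N8 is 1.00, 1.25 and 1.50 when N20/N8 is 1, 0.5 and 0.

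**Step 3: size under assumed fading.** Take exponential fading with N1 = 1. Example, half-life 12 weeks: N8 = 2^(−7/12) = 0.667 and N20 = 0.315–0.354. The contrast is 0.824–0.843, which is 24–26% above N8. N13 = 0.472–0.530, so the 1-week contrast is 1.07–1.10.

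| Assumed half-life | N8 as share of N1 | 8-week overstatement | 1-week overstatement |
|---|---|---|---|
| 8 weeks | 55% | 31–34% | 8–11% |
| 12 weeks | 67% | 24–26% | 7–10% |
| 24 weeks | 82% | 14–16% | 4.5–6.5% |
| 52 weeks | 91% | 7–8% | 2–4% |

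At a 12-week half-life, true 8-week retention of 67% would appear as about 0.824/1.07 = 77%. The absolute excess, 0.5·(N8 − N20), peaks at 0.17–0.18 of the 1-week effect, at a half-life near 8 weeks.

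**Step 4: the three planned models.** Treatment plus period returns 1.5·N8 − 0.5·N20 at any allocation split. Treatment-only does so at 1:1. With a share f in tDCS-first and no period effect it returns (1 + f)·N8 − f·N20, so its ceiling is 1.4 to 1.6 times N8 for f = 0.4 to 0.6. The carryover model returns the same quantity if its effect is averaged over orders, and N8 if it is read from period 1.

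Model selection was simulated with 44 participants, an effect of 0.6, SD of change about 1.0, 0.7 or 0.5, and 1,000 runs each:

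| Fade by Visit 38 | Carryover model selected | Mean estimate / N8, averaged reading | Mean estimate / N8, period-1 reading |
|---|---|---|---|
| None | 4–5% | 1.00–1.01 | 1.00–1.01 |
| Half | 13–51% | 1.24–1.26 | 1.07–1.17 |
| All | 50–98% | 1.48–1.51 | 0.98–1.17 |

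**Step 5: separate trained lists.** If each period had its own verbs, only generalisation (G) would reach the second baseline. The contrast would be N8 + 0.5·(G8 − G20), so only the generalised part could bias it.

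**The case against.** **The plan already has a carryover model.** True, and read from period 1 it removes most of the bias. A reader might infer that the planned estimate always equals 1.5·N8 − 0.5·N20. It does not. But the carryover model is used only if it wins on R-squared, and the plan does not say which of its coefficients is the tDCS effect, so the protection is not secured.

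**A reader might infer a 50% overstatement.** That limit is approached only if nearly all of the 8-week effect is gone by Visit 38. No half-life in the table exceeds 34%. Under exponential fading, a percentage near 50% arises only when the 8-week effect is itself small.

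**Trained verbs are the weak case.** With separate lists the formula fails. With one list, the verbs are retrained for 15 sessions between Visits 21 and 38 on a bounded score. Retraining or a ceiling could bring both orders to the same level, making D38 zero and removing the bias. This stands. The formula is safest for the nouns, which do not depend on the trained-verb split.

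**A washout and a sustained effect are not contradictory.** Agreed. Change scores subtract the Visit 21 level, so a gain that persists unchanged to Visit 38 does no harm. Only fading after Visit 21 matters.

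**The planned contrast is more precise.** This also stands. In further simulations (45 participants, several error structures, no loss before Visit 21), nominal 95% intervals covered N8 in 91–93% of trials at half fade. That implies a bias of about 0.4–0.6 standard errors, or a root-mean-square error of √(1 + 0.4²) to √(1 + 0.6²) = 1.08–1.17 standard errors. The Visit 21 difference has a standard error of 1.02 to 1.83 times the planned one, depending on structure. At half fade or less, the planned contrast is often as accurate or more so, and the documents give no ground for discarding it.

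**Conclusion.** The point holds in conditional form. Because of Visit 21's double role, the order-averaged 8-week contrast is D21 − D38/2, and it overstates a real tDCS effect that fades between Visits 21 and 38. The size depends on a fade rate that the documents do not give, so the tabulated 7–34% at 8 weeks and 2–11% at 1 week are illustrations under assumed half-lives.

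The result rests on additive gains, the same scored items in both periods, fading unaffected by retraining and, for the treatment-only model, 1:1 allocation. It applies to two of the three planned models, and to the third if its effect is averaged over orders. There is no bias if nothing fades after Visit 21, if both orders reach the same level at Visit 38, or if there is no true effect.

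A reader might infer that false positives are inflated or that the trial's main result is undermined. Neither follows. With no effect there is nothing to fade, and section 7a makes the 1-week change primary, where the distortion is smaller. This is an estimation problem in a secondary analysis, and it matters for any statement about sustained benefit.

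**What to change.** Rewrite the 8-week paragraph of section 7c as follows.

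1. Keep the planned contrast, but do not call it the 8-week effect without qualification. State that Visit 21 is not assumed to be a washed-out baseline.
2. Report beside it, with confidence intervals, the order difference at Visit 21 adjusted for the first baseline (the 8-week effect free of this bias) and the order difference at Visit 38. A negative Visit 38 difference indicates overstatement by half its size.
3. State in advance that, if the carryover model is selected, the tDCS effect is read from period 1.
4. State whether one trained list is used in both periods.
5. Qualify any claim of sustained benefit when the planned contrast and the Visit 21 difference disagree.

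**Cost.** One paragraph, with no extra visits, tests or participants. The Visit 21 difference is less precise. Its standard error is 1.02–1.14 times that of the planned contrast with independent test error, 1.35–1.40 times if participants also differ strongly in rate of decline, and 1.83 times in the worst structure tried. For a comparison with 80% power (two-sided 5% assumed), power becomes Φ(2.80/ratio − 1.96): about 69% at a ratio of 1.14, 52% at 1.40 and 33% at 1.83. It should therefore accompany the planned contrast and not replace it, and a non-significant Visit 21 difference should not be read as loss of effect.
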